OFFICIAL TITLE OF STUDY: Attention Bias Modification Training in Youth With Subthreshold Impairing Anxiety

NCT NUMBER: 02410967

DATE: 04-05-2018

PROTOCOL

Over the past three decades, substantial advances have been made in knowledge about treating children and adolescents who suffer from diagnosable anxiety disorders¹. The knowledge landscape is bleaker when it comes to youth who do not have diagnosable anxiety disorders but instead experience subthreshold impairing anxiety (SubImpAnx). There is a critical need to develop evidence based interventions for youth with SubImpAnx given its high prevalence², the significant concurrent impairment and distress associated with SubImpAnx^{2,3} and the high risk of escalation from SubImpAnx to diagnosable anxiety disorders^{4,5}.]

The small number of intervention studies that have addressed SubImpAnx have not focused exclusively on SubImpAnx. Further, the interventions examined were traditional, resource intensive approaches (e.g., CBT)⁶⁻⁸. Even when it comes to diagnosable disorders, traditional approaches to mental health service delivery for youth cannot meet current demand⁹⁻¹². The inadequacies of traditional service delivery are magnified for impaired but undiagnosed youth. The economic challenges the U.S. faces render even more urgent the need to move beyond traditional service delivery toward developing and evaluating 'least restrictive' interventions to address SubImpAnx in terms of impact on patients (i.e., cost and personal investment) and therapists (i.e., training and treatment delivery)¹³. Efforts such as computer assisted and web based cognitive behavioral therapy for anxiety disorders represent promising directions¹⁴⁻¹⁷. It is an unaddressed empirical question whether a least restrictive treatment can reduce SubImpAnx in youth.

This application represents an initial step to address this question by collecting pilot data on a novel least restrictive treatment rooted in neuroscience among youth with SubImpAnx: Attention Bias Modification Training (ABMT). Substantial evidence from behavioral and neuroscience research documents a threat related attention bias in anxiety¹⁸⁻²⁰, including subthreshold anxiety in youth²¹⁻²⁴. Attention bias to threat occurs in response to stimuli presented very rapidly and corresponds to perturbations in amygdala-prefrontal circuitry²⁴⁻³⁰. ABMT is the direct translational treatment implication of attention bias to threat. ABMT targets attentional threat bias via computer based training that affects subcortically based and frontal-cortical networks²⁸.

No research has examined ABMT among youth with SubImpAnx. Given evidence of consistent attention bias across youth with subthreshold anxiety²¹⁻²⁴ and youth with anxiety disorders³¹⁻³³, it is reasonable to hypothesize an anxiety reduction effect of ABMT among youth with SubImpAnx. If effective, ABMT would represent a least restrictive treatment option for youth with SubImpAnx with respect to patient impact in that it is low-cost, brief, and portable, and with respect to therapist impact in that it does not require skilled clinicians.

This UH2 study will enroll [66] clinic referred youth ages 8-16 years who do not meet DSM-IV diagnostic criteria for anxiety disorders but instead have SubImpAnx. [50 youth will be enrolled at the FIU Child Anxiety & Phobia Program and an additional 16 youth will be enrolled at the Yale Child Study Center]. These youth will be randomly assigned to 8 sessions of either ABMT or a placebo control (PC) task over 4 weeks. Clinician ratings on youth anxiety symptoms and impairment will be evaluated as the primary outcome. Parent ratings and youth self ratings on anxiety symptoms and impairment will be evaluated as secondary outcomes. Measures will be collected at pretreatment, immediate posttreatment (post), and 8 week followup. The following aims will be addressed:

Aim 1: Collect pilot data on the effects of ABMT and a PC task on levels of anxiety and impairment at post. A multisource assessment approach will be used to preliminarily examine anxiety and impairment reduction among youth in the ABMT condition as compared to youth in the PC task condition at post.

Aim 2: Collect pilot data on the effects of ABMT and a PC task on levels of anxiety and impairment at a follow up evaluation 8 weeks after the post evaluation. This will provide initial data regarding the maintenance of ABMT effects 8 weeks after treatment ends. A multisource assessment approach will be used to preliminarily examine anxiety and impairment reduction among youth in the ABMT condition as compared to youth in the PC task condition at the 8 week follow up.

Aim 3: Preliminarily examine whether ABMT leads to lower levels of attention bias toward threatening stimuli as compared to a PC task at a post evaluation and at a follow up evaluation 8 weeks after post. Reductions in attention bias to threat have been theorized to mediate ABMT's anxiety reduction effect^{34,35}. Data from this UH2 will allow us to gain perspective on the theoretical underpinning of ABMT and will inform decisions about whether to pursue attention bias as a mediator in a subsequent R01.

Aim 4: Describe the course of anxiety symptoms and impairment during treatment among youth in the ABMT condition. Youth anxiety symptoms and impairment will be assessed at pre and every other session (i.e., sessions 2, 4, 6, 8), and post. We will explore the trajectory of anxiety symptoms and impairment across these six assessment waves in an effort to gain initial insight into 'dosage' related issues of ABMT.

APPROACH

See Figure 1 for the randomized, double blind, placebo controlled design. After a pre assessment, participants will be randomly assigned to either ABMT or Placebo Control (PC) Task.

In ABMT, participants will complete 8 sessions of ABMT. In PC, participants will complete 8 sessions of a PC task. Number and duration of sessions will be identical in both conditions. All participants will complete the Columbia Impairment Scale and Screen for Child Anxiety Related Emotional Disorders after even numbered sessions. A week after session 8, all participants will complete a post assessment. After post, no training or assessment will be administered for 8 weeks. Participants then will complete a follow up assessment. After the follow up, participants in the PC condition will be offered ABMT. All participants will be offered further treatment resources as needed (see Human Subjects). Total duration from pre to follow up will be ~12-14 weeks.

Participants. [66] youth (8-16 years) will be admitted.

Inclusion Criteria. (A) Youth and parents must endorse youth SubImpAnx; and (B) if youth have ADHD, mood disorders, tics, or impulse control problems, those disorders must be treated with medication and be stabilized.

[figure not shown]
Exclusion Criteria. For youth to be excluded, they must (A) meet diagnostic criteria for Organic Mental Disorders, Psychotic Disorders, Pervasive Developmental Disorders, or Mental Retardation; (B) show high likelihood of hurting themselves or others; (C) not be living with a primary caregiver who is legally able to give consent for participation; (D) be a victim of previously undisclosed abuse requiring investigation by Department of Social Services; (E) be involved currently in a psychosocial treatment; (F) have a serious vision problem that is not corrected with prescription lenses; or (G) have a physical disability that interferes with their ability to click a mouse button rapidly and repeatedly.

Treatment Conditions. Consistent with past ABMT trials^{76,77}, participants will complete 15-minute ABMT or PC task sessions 2X a week for 4 weeks. At each session, participants will complete 160 trials of either the ABMT task or the PC task. In both tasks, a fixation cross will appear first, followed by 2 faces of the same actor, one above the other. One face will depict the actor emoting an angry expression and the other will depict the actor emoting no expression. After presentation of the faces for 500ms, a probe (< or >) will appear in the location of one of the faces. Participants will indicate the type of probe (< or >) by pressing either the left or the right mouse button. The probe will remain on the screen until participants respond. After responding, the next trial will begin. **ABMT Task:** In this task, the probe will replace the neutral face on 100% of trials. On 80% of trials, angry face location will predict probe location (i.e., in the location opposite the angry face). On these trials, angry face location and actor will be fully counterbalanced. Probe type will appear with equal probability for angry face location and actor. On the other 20% of trials, participants will see neutral-neutral face pairs. **Placebo Control (PC) Task:** The PC task will be identical to the ABMT task except for the frequency with which the probe replaces the neutral face. 80% of trials include one neutral face and one angry face. On these trials, angry face location, probe location, and actor are fully counterbalanced. Probe type appears with equal probability for angry face location, probe location, and actor. The other 20% of trials include neutral-neutral face pairs. The PC task is an ideal control condition because it is robust to differential expectancy effects⁸⁴.

Measures. See Figure 1 for the assessment schedule. Each assessment will be conducted in single sessions at our clinics by carefully trained graduate research assistants.

I. Primary Outcome: Pediatric Anxiety Rating Scale (PARS)⁹³. The PARS is a widely used, reliable, and valid measure of global anxiety symptoms and impairment in youth ages 6-17. At the pre assessment, the interviewer who conducts the ADIS-C/P and PARS interviews will complete the rating. At post and follow up, an independent evaluator blinded to the patient's treatment condition will complete the PARS.

II. Secondary Outcomes: Youth Impairment, Youth Anxiety Symptoms. Youth impairment and anxiety symptoms will be assessed from the youth and parent perspectives using the respective versions of the **Columbia Impairment Scale (CIS-C/P)⁹⁴** and the **Screen for Child Anxiety Related Emotional Disorders (SCARED-C/P)^{95,96}**. The CIS is a reliable and valid global impairment scale for youth^{94,97}. The SCARED is a widely used, psychometrically sound measure of youth anxiety^{95,96,98,99}.

III. Attention Bias to Threat will be assessed with a probe-detection task identical to the PC task, except that a unique set of faces will appear in this task⁷³. Scores are calculated by subtracting response times when the probe appears at neutral face location from response times when the probe appears at angry face location.

IV. Maintenance of Blind. We will determine maintenance of the blind by asking youth participants and their parents at follow up whether they believed the youth was in either the ABMT or PC condition.

V. Inclusionary Measures. **a. ADIS-C/P**⁹². Youths and parents will be administered the ADIS-C/P to determine SubImpAnx status as described in Inclusion Criteria. **b. Treatment Utilization**¹⁰⁰. Medication and psychosocial treatment utilization will be assessed at pre, post, and follow up to identify new treatment families may start during their participation in the UH2 (we will request they not alter treatment during the study).

STATISTICAL ANALYSIS PLAN

Data management protocols will be used to ensure data integrity. Missing values will be estimated using Markov chain Monte Carlo multiple imputation algorithms based on the Gibbs sampler. Analyses will focus on least squares test (OLS) of means and modern robust estimation procedures¹⁰¹ that rely on Wilcox's R routines¹⁰². We will examine associations between condition and baseline variables to ensure successful randomization and will use a Holm adjusted Bonferroni method to control experimentwise error rates¹⁰³.

Aim 1: Preliminarily examine whether levels of anxiety and impairment at post are lower for youth in ABMT as compared to youth in PC. The OLS analysis is a 2 group single degree of freedom contrast between the ABMT and the PC conditions using pre scores as a covariate to increase statistical power. The contrast focuses on the comparison of adjusted means at post. Of interest is whether the contrast between conditions is statistically significant for independent evaluator rated anxiety symptoms and impairment (PARS; **Primary Outcome**), parent ratings on youths' anxiety symptoms (SCARED-P) and impairment (CIS-P) (**Secondary Outcome**), and youth self ratings on anxiety symptoms (SCARED-C) and impairment (CIS-C) (**Secondary Outcome**).

Aim 2: Preliminarily examine whether levels of anxiety and impairment at 8 week follow up are lower for youth in ABMT as compared to youth in PC. The analytic approach will be identical to Aim 1, except that contrasts will focus on scores at the follow up evaluation instead of the post evaluation.

Aim 3: Preliminarily examine whether ABMT, as compared to PC Task, leads to lower levels of attention bias to threat at post and follow up. The analytic approach will be identical to Aims 1 and 2, except that contrasts will focus on scores on the attention bias task instead of scores on anxiety symptoms and impairment.

Aim 4: Describe the course of anxiety symptoms and impairment during treatment among youth in the ABMT condition. Youth anxiety symptoms and youth impairment will be assessed at pre, ABMT sessions 2, 4, 6, 8, and post. These 6 assessments waves can be used to gain insight into the timing of ABMT response. This analysis will be approached from a latent growth modeling framework. In separate analyses, we will model the trajectory of anxiety symptoms (SCARED-C/P) and impairment (CIS-C/P). Models of no growth, linear change, and quadratic change will be explored in an effort to identify the best fitting trajectory. We will use growth modeling variants that are amenable to small sample sizes¹⁰⁸.

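### The attention-bias score is defined so that more bias toward threat gives a lower score, yet Aim 3 looks for lower bias on these scores and gives no sign rule

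*Combined protocol and SAP*

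**What the plan says.** Item III of the Measures section assesses attention bias with a probe-detection task built like the PC task but with a different set of faces. It describes the score as "calculated by subtracting response times when the probe appears at neutral face location from response times when the probe appears at angry face location".

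Aim 3, in the list of aims, asks "whether ABMT leads to lower levels of attention bias toward threatening stimuli as compared to a PC task". It adds that the data will "inform decisions about whether to pursue attention bias as a mediator in a subsequent R01". The SAP's Aim 3 repeats the question, asking whether ABMT "leads to lower levels of attention bias to threat at post and follow up". It carries over the approach of Aims 1 and 2, except that "contrasts will focus on scores on the attention bias task instead of scores on anxiety symptoms and impairment". That approach is a single-degree-of-freedom OLS contrast between conditions, "using pre scores as a covariate to increase statistical power". In Aim 1 the question is "whether levels of anxiety and impairment at post are lower for youth in ABMT as compared to youth in PC", and Aim 2 asks the same at follow up.

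Neither the protocol nor the SAP says what a positive or negative bias score means, or that the score is reversed before analysis.

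**The concern.** The measure is named for bias toward threat, and Aim 3 counts a lower level of it as success. A reader would expect a higher score to mean more bias, as a higher level is worse in Aims 1 and 2. The written formula produces the opposite. An analyst who computes the score as defined and then looks for a lower adjusted mean in ABMT would be looking for more bias toward threat.

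Direction is the substance of Aim 3. The aims section gives the theory that reduced threat bias mediates the anxiety benefit, and it makes these data an input to whether bias is pursued as a mediator in the R01. With the sign reversed, supportive data would look contrary and contrary data supportive.

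**Working it through.** The documents give no effect size, variance, power or alpha for this measure, so there is no stated figure to reproduce. The check concerns the sign of a difference score.

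**1. The formula.** Subtracting A from B is B − A. The score as written is therefore S = RT(probe at angry face) − RT(probe at neutral face).

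**2. How S moves with bias.** Let v be the speed-up, in ms, at the angry location relative to the neutral one, so larger v means more bias toward threat. Around an assumed mean response time of 600 ms, RT(angry) = 600 − v/2 and RT(neutral) = 600 + v/2, so S = −v:

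| v (bias toward threat) | S as written | S reversed (neutral − angry) |
|---|---|---|
| −20 | +20 | −20 |
| 0 | 0 | 0 |
| 20 | −20 | +20 |
| 40 | −40 | +40 |

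The score as written falls as bias rises. The 600 ms cancels and does not matter.

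**3. How training moves S.** Under Treatment Conditions, in the ABMT task "the probe will replace the neutral face on 100% of trials". Training of this kind should make responses at the neutral location relatively faster. RT(neutral) then falls relative to RT(angry), and S rises.

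**4. What reversing the score does to the planned contrast.** The carried-over model is S_post = b0 + b1·G + b2·S_pre + e, where G = 1 for ABMT. Multiplying through by −1 gives −S_post = −b0 − b1·G + b2·(−S_pre) − e. The condition coefficient changes sign. The slope on the pre score, the residual variance, the standard error, |t| and the two-sided p do not change.

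**5. Illustration with assumed values.** One data set was simulated with the planned 66 youth, assumed to split 33 per arm. True bias (neutral − angry) at pre had mean 20 ms and SD 30 ms. Post bias was 0.3 × pre plus noise with mean 14 ms and SD 30 ms, less 20 ms in ABMT. Residual df = 66 − 3 = 63.

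| Scoring | ABMT − PC, ms | t | Two-sided p |
|---|---|---|---|
| As written (angry − neutral) | +18.2 | +2.52 | 0.014 |
| Reversed (neutral − angry) | −18.2 | −2.52 | 0.014 |

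Training reduced bias in this data set by construction. Scored as written, the result appears as a higher value in ABMT, which a literal reading of Aim 3 would report as more bias. The plan does not state whether tests are one- or two-sided. A one-sided test of ABMT lower than PC would give p = 0.993 as written and p = 0.007 reversed.

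**The case against.** The strongest reply is that the text contains no contradiction. The Measures section defines a score, while Aim 3 states a hypothesis about a construct and never says that a lower score is expected. An analyst who knows the task can satisfy both by reading a less negative score as less bias. This reading is available, and the error arises only if the formula and the word lower are both applied literally. But nothing in the plan directs the analyst to that reading. The SAP puts the contrast on the raw scores under the approach used for outcomes where lower is better.

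Second, the documents do not state that attention to the angry face speeds responses there, and the source cited for the task might give a sign convention. The premise is indeed unstated, but it is the logic of a probe task, and the ABMT design in Treatment Conditions depends on it. The cited source cannot be checked here, and a convention found only there would still conflict with the formula or need to be stated in the plan.

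Third, two-sided inference is unaffected, Aim 3 is preliminary, and attention bias is listed outside the primary and secondary outcomes. All of this is correct and limits the size of the problem. The simulation also only displays an algebraic identity, and its magnitudes say nothing about this trial. What remains is a wrong direction on the only measure Aim 3 has.

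**Conclusion.** The concern holds. The score as defined runs opposite to the wording of Aim 3, and no sign rule or recoding connects the two. Followed literally, the plan reverses the direction of two contrasts (post and follow up) and of the evidence on bias as a mediator.

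The effect is on sign alone. Absolute effect size, two-sided p-value and power are unchanged, and the PARS primary outcome, the SCARED and CIS secondary outcomes and the sample size are not involved. The conclusion rests on one premise from outside the text, that attention at a location speeds the response to a probe there. The response times, SDs and effect in the illustration are assumptions, and the sign result does not depend on them. This should be fixed, because a sign settled at analysis cannot be shown to have been chosen before the data were seen.

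**What to change.** Either of two one-sentence changes resolves it.

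- **Reverse the subtraction in Measures, item III:** *Bias score = RT with the probe at the neutral face minus RT with the probe at the angry face; positive scores indicate bias toward threat.* Lower in Aim 3 is then correct for both contrasts.
- **Keep the formula and add to Aim 3:** *More negative scores indicate more bias toward threat; the hypothesis is a higher adjusted mean score in ABMT than in PC.*

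The first lets bias be read in the same direction as the other outcomes. The second leaves the existing definition alone. Whichever is chosen, the scoring code should be checked against it before the bias data are analysed by condition. Neither change needs new data or alters the test, alpha or sample size.

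### Does the Holm clause, which lists no family of tests, leave the primary PARS result open to choice?

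*Combined protocol and SAP*

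**What the plan says.** The opening paragraph of the Statistical Analysis Plan has one sentence on multiplicity. Its first half reads "We will examine associations between condition and baseline variables to ensure successful randomization"; its second half says the investigators "will use a Holm adjusted Bonferroni method to control experimentwise error rates". No family, number of tests or testing order is given. The same paragraph says "Analyses will focus on least squares test (OLS) of means and modern robust estimation procedures".

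The aims then set out the contrasts. For Aim 1, "The OLS analysis is a 2 group single degree of freedom contrast between the ABMT and the PC conditions", with the pre score as covariate, and "Of interest is whether the contrast between conditions is statistically significant for independent evaluator rated anxiety symptoms and impairment" (PARS, labelled primary) and for the parent and youth SCARED and CIS scores (labelled secondary). For Aim 2, "The analytic approach will be identical to Aim 1, except that contrasts will focus on scores at the follow up evaluation". For Aim 3, "The analytic approach will be identical to Aims 1 and 2, except that contrasts will focus on scores on the attention bias task".

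The protocol overview says "Clinician ratings on youth anxiety symptoms and impairment will be evaluated as the primary outcome", without singling out a time point. In the SAP the primary label is attached to PARS in Aim 1, which concerns scores at post.

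**The concern.** Holm's procedure needs a list of hypotheses, because each p value is compared with alpha divided by the number of hypotheses still standing. With no list, several families can be read into the text: the Aim 1 to 3 contrasts together, each aim separately, each time point separately, the secondary contrasts only, or even the baseline checks only, since they share the sentence. Counting the robust analyses as tests in their own right would double the number.

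The readings differ in effect. A wide family controls error but makes PARS at post compete on equal terms with the other measures. A narrow family protects PARS but does not control error across the whole set of contrasts. If the choice were made after the data were seen, it could decide whether the primary outcome is called significant. Aim 1 does ask about statistical significance, so the question is a fair one.

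**Working it through.** **Inputs from the documents.** Sample size 66 (protocol overview); the outcomes and time points in SAP Aims 1 to 3; pre scores as covariate (SAP Aim 1). The plan states no alpha, power, effect size or allocation ratio, so there is no figure of its own to reproduce.

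**Assumptions.** Two-sided 0.05; 33 per arm; pre-post correlation r = 0.5; correlation 0.4 between test statistics; no dropout unless stated.

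**Step 1, count the contrasts.**
- Aim 1: PARS, SCARED-P, CIS-P, SCARED-C and CIS-C at post = 5.
- Aim 2: the same five at follow-up = 5.
- Aim 3: attention bias at post and follow-up = 2.
- Total 5 + 5 + 2 = 12.

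**Step 2, where the reading can matter.** The first Holm threshold is 0.05/m: 0.05 for m = 1, 0.01 for m = 5, 0.00417 for m = 12. A PARS-at-post p at or below 0.00417 is significant on every reading up to 12 tests, and one above 0.05 on none. In between, rank decides. For p = 0.02, 0.05/0.02 = 2.5, so it passes only when at most two hypotheses remain. In a five-test family, at least three of the other four must already have been rejected; in a 12-test family, at least ten of the other eleven.

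**Step 3, power for PARS at post.** Noncentral t with 66 − 3 = 63 df and noncentrality d/√(1 − r²) × √(33/2). For d = 0.6 this is 0.6/√0.75 × √16.5 = 2.81.

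| d | Alone at 0.05 | First step of 12-test Holm |
|---|---|---|
| 0.5 | 63.7% | 27.6% |
| 0.6 | 79.1% | 44.3% |
| 0.8 | 95.9% | 77.8% |

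The first-step figure is close to the full Holm power when only PARS at post responds. If all 12 contrasts share d = 0.6, full Holm gives 55.6% (100,000 simulated trials). So PARS is significant alone but not in the family in 79.1 − 55.6 = 23.5% to 79.1 − 44.3 = 34.8% of such trials. The gap persists under other inputs at d = 0.6: first-step power is 34.7% against 71.1% alone for r = 0.3, 66.9% against 91.9% for r = 0.7, and 35.5% against 72.1% with 28 analysed per arm.

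**Step 4, error over the 12 contrasts when no effect exists.**

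| Reading | Independent tests | Correlation 0.4 (simulated) |
|---|---|---|
| One 12-test Holm family | 5% | 4% |
| Holm per time point | 1 − 0.95² = 10% | 8% |
| Holm per aim | 1 − 0.95³ = 14% | 12% |
| Baseline checks only | 1 − 0.95¹² = 46% | 36% |

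Only the first row delivers what the SAP's word "experimentwise" promises. The other rows describe readings that set that word aside.

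**Step 5, the alternative.** Suppose PARS at post is tested first at 0.05, and Holm is applied to the other 11 contrasts only if it succeeds. PARS keeps 79% power and error stays near 5%. Power for each other responding contrast (d = 0.6, simulated) becomes:

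| Which contrasts respond | One 12-test Holm family | PARS tested first |
|---|---|---|
| All 12 | 56% | 50% |
| All except PARS at post | 53% | 3% |
| Attention bias only | 45% | 2% |

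**The case for a change.** The strongest case for a change is that every reading has a fault. If PARS at post belongs to the 12-test family, it loses 23 to 35 percentage points of power at d = 0.6. If it is tested at 0.05 outside the family, error is no longer controlled over the whole set. A plan that promises error control and asks about significance should say which applies, and doing so costs a few words. Calling PARS primary neither exempts it from adjustment nor places it first, and the label in the protocol overview names no time point. The role of the robust analyses is also not stated.

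Part of this stands. The family is not written down, PARS has no stated place in the Holm sequence, and the arithmetic is right.

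The rest carries less weight. The power loss on the wide reading is the ordinary price of Holm, and paying it is a legitimate choice in a multisource pilot. The high error rates need readings that contradict the SAP's own term; the baseline-only reading rests on nothing more than a shared sentence. Doubling the count to 24 is strained, because Aim 1 names the OLS contrast as the analysis, Aims 2 and 3 repeat it, and no separate robust hypothesis is listed. Nothing in the documents suggests that the family would be chosen after seeing the data.

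**Conclusion.** No change to the plan follows. What is missing is a list that an analyst can draw up from Aims 1 to 3: the 12 between-group OLS contrasts form the family, and the robust results are read beside them. On that reading the promised error control is met.

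The uncertainty is confined to a PARS-at-post p value between about 0.004 and 0.05, given alpha 0.05 and a family of 12. The consequence is limited because the aims are described as preliminary and no success or go/no-go rule uses PARS significance.

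The one substantive alternative, making every other contrast depend on PARS at post, would not clearly improve the plan. It raises PARS power but nearly removes the chance of a formal finding elsewhere when PARS does not respond. That includes Aim 3, a separate question about mechanism meant to inform a later grant application. Statisticians may reasonably differ on that choice.

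The power figures rest on assumed alpha, allocation, effect sizes and correlations. They show what Holm costs under those inputs, not the size of a defect in this plan. The conclusion itself rests on the ordinary meaning of experimentwise control and on the pilot purpose.

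### Aim 4 reads the timing of ABMT response from the ABMT arm alone, although PC youth give the same scores at the same sessions and no stated analysis uses them

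*Combined protocol and SAP*

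**What the plan says.** The SAP states Aim 4 as "Describe the course of anxiety symptoms and impairment during treatment among youth in the ABMT condition". SCARED-C/P and CIS-C/P are to be modelled separately over pre, sessions 2, 4, 6 and 8, and post: "Models of no growth, linear change, and quadratic change will be explored in an effort to identify the best fitting trajectory". The only further specification is "We will use growth modeling variants that are amenable to small sample sizes".

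Two sentences go beyond description. The SAP says "These 6 assessments waves can be used to gain insight into the timing of ABMT response". The protocol's own statement of Aim 4 says the trajectory is explored "in an effort to gain initial insight into 'dosage' related issues of ABMT".

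The Approach section shows that the control data exist: "All participants will complete the Columbia Impairment Scale and Screen for Child Anxiety Related Emotional Disorders after even numbered sessions". It also makes the number and length of sessions the same in both conditions. The arms are compared elsewhere, but not at these sessions. For Aim 1, "The contrast focuses on the comparison of adjusted means at post"; Aim 2 does the same at follow-up; Aim 3 uses the attention bias task at post and follow-up.

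**The concern.** Timing of response to ABMT is a statement about what ABMT did and when. The Aim 4 curve shows what happened to youth who received ABMT, which is ABMT response plus whatever would have happened anyway. Youth are clinic referred and enter because they and their parents endorse impairing anxiety, so some regression to the mean is plausible. Repeated questionnaires and clinic visits may also move the scores.

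The randomised PC arm is what removes this shared change, and Aim 4 leaves it out. Aim 1 can show whether the arms differ at post, but not when a difference arose. A shared steady fall could be read as steady response to ABMT. A shared drop concentrated at the first retest could be read as early response that then levels off. Because this is a pilot intended to inform later work, such a reading could be carried forward.

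**Working it through.** **Which scores enter which analysis**

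| Scores | ABMT | PC |
|---|---|---|
| SCARED and CIS at pre and post | Aims 1 and 4 | Aim 1 |
| SCARED and CIS at sessions 2, 4, 6, 8 | Aim 4 | none stated |
| SCARED and CIS at follow-up | Aim 2 | Aim 2 |

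The PC session scores might enter the multiple imputation, but the plan does not say so, and that would not be an analysis of the PC course.

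**Inputs for an illustration**

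- From the documents: 66 youth; six waves; two sessions a week, with post a week after session 8, so the waves are about weekly (0 to 5).
- Assumed, because the documents give none of them: 33 per arm, pre SD 1, ICC 0.6 (residual variance 0.4), between-youth slope SD 0.06 per wave, no ABMT effect, and a shared fall of *d* SD from pre to post.

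**Shared linear fall.** The per-youth slope has variance 0.06² + 0.4/17.5 = 0.02646, where 17.5 is the sum of squares of the centred times. The standard error of the mean slope is √(0.02646/33) = 0.0283. For *d* = 0.3 the mean slope is −0.3/5 = −0.06, the noncentrality is 0.06/0.0283 = 2.12, and the one-sample t-test on 32 df is significant in 54% of trials.

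**Shared drop wholly at the first retest.** The quadratic contrast is (5, −1, −4, −4, −1, 5), with sum of squares 84. A drop of *d* at every wave after pre gives a contrast of 5*d*. Its standard error is √(0.4 × 84/33) = 1.009. For *d* = 0.5 the noncentrality is 2.5/1.009 = 2.48, giving 67%. If half the drop is at the first retest and half is linear, the contrast halves.

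| Shared fall (SD) | ABMT-only slope, linear fall | ABMT-only curvature, all at first retest | ABMT-only curvature, half and half |
|---|---|---|---|
| 0.2 | 28% | 16% | 8% |
| 0.3 | 54% | 30% | 11% |
| 0.4 | 78% | 49% | 16% |
| 0.5 | 93% | 67% | 23% |

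Under the linear fall, curvature is significant in only 5%, so no false timing shape arises. The arm-by-time and arm-by-time-squared tests reject in about 5% in every row, because shared change cancels.

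**Sensitivity.** With 26 per arm, the slope column becomes 23%, 44%, 67% and 85%, and the first-retest column 14%, 25%, 39% and 56%. With 33 per arm and ICC 0.5 to 0.7, the 0.5 SD first-retest figure runs from 58% to 79%. Over the same ICCs and slope SD 0.03 to 0.10, the 0.3 SD linear-slope figure runs from 40% to 70%.

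**What a two-arm analysis could show for a true 0.5 SD ABMT effect.** The between-arm standard error of the quadratic contrast is √(2 × 0.4 × 84/33) = 1.427.

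| Form of effect | Contrast | Power, 33 per arm | Power, 26 per arm |
|---|---|---|---|
| Gradual, complete by session 4, or arising only after session 6 | ±2.25 | 34% | 28% |
| Abrupt at session 4 or session 8 | ±2.0 | 28% | 23% |
| Abrupt at session 6 | 0 | 5% | 5% |

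A step at session 6 falls at the midpoint of the six waves, so its quadratic contrast is zero.

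For one session's ABMT minus PC difference adjusted for pre, the residual variance at wave *k* is 1 + 0.0036*k*² − 0.36. This is 0.644 at session 2 and 0.698 at session 8. The 95% interval is about ±0.40 to ±0.41 SD with 33 per arm, and ±0.45 to ±0.47 SD with 26.

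These differences should not be read off a fitted quadratic. With an abrupt 0.5 SD effect from session 4, the joint quadratic with a common pre mean gives on average −0.24 SD at session 2, where the true difference is 0.

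**The case against.** The strongest reply is that Aim 4 claims little. It is worded as description and exploration in a pilot, no test or decision rests on it, and the controlled comparisons are in Aims 1 to 3. This stands, and it limits the weight of the point. It does not cover the sentences on timing and dosage, which credit the change to ABMT.

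Second, the 28% to 93% slope rates detect real change and carry no false timing shape. That is right. They mislead only if the change is attributed to ABMT.

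Third, the curvature rates depend on an early-concentrated drop and on how the growth models are compared. This also stands. The plan names neither a selection criterion nor a random-effects structure. With the whole 0.5 SD drop at first retest, BIC chose the quadratic in 75% of 400 simulated trials when only a quadratic mean was added, and in 17% when a full random quadratic factor was added. At 0.3 SD the figures were 35% and 1.5%. The 67% is therefore one point in a wide range. The plan's small-sample growth variants were not simulated.

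Fourth, the remedy has low power for timing, and a sentence calling the curve uncontrolled would be cheaper. Such a sentence would prevent the misreading, but it would leave the timing question without any controlled estimate although the data for one are in hand.

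**Conclusion.** The point holds and is worth considering. The gap is plain in the text and needs no assumption: the PC session scores are collected, no stated analysis uses them, and the ABMT-only curve cannot attribute the timing of change to ABMT. How far this would mislead is uncertain, because allocation, ICC, slope SD and shared change are all assumed and the growth-model specification is open. A steady shared fall creates no false shape; an early-concentrated one can. The ABMT-only curve remains a valid description of change. One exploratory aim is affected, and no primary or secondary contrast changes.

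**What to change.** Amend Aim 4 in the SAP as follows.

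- Fit the growth models to both arms jointly, with a common pre mean and condition-by-time and condition-by-time-squared terms.
- Report ABMT minus PC differences with 95% intervals at sessions 2, 4, 6 and 8, estimated with session as a category, and base any timing statement on them.
- Leave the post contrast to Aim 1 as the reference result.
- Label the 16 intervals (4 scales × 4 sessions) exploratory, unadjusted and outside the family for which the SAP "will use a Holm adjusted Bonferroni method to control experimentwise error rates".
- Keep the ABMT-only curve, labelled as uncontrolled change.
- State that all youth follow one schedule, so the differences show the effect to date and cannot separate number of sessions from elapsed time. State also that precision for timing is low.

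The cost is SAP wording, one joint model per scale and 16 exploratory intervals; no new data are needed. The change removes confounding with shared change. At this sample size it will often not settle timing, and it cannot answer the dosage question.
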